7.2. Participant Withdrawal From the Study

A participant may withdraw from the study at any time at their own request, or may be withdrawn at any time at the discretion of the investigator for safety, behavioral, compliance, or administrative reasons.

If a participant withdraws from the study, they may request destruction of any samples taken and not tested, and the investigator must document this in the site study records. If the participant withdraws consent for disclosure of future information, the sponsor may retain and continue to use any data collected before such a withdrawal of consent. See Table 3, Table 4, and Table 5 for data to be collected at the time of study withdrawal and follow-up and for any further evaluations that need to be completed.

7.3. Lost to Follow-Up

A participant will be considered lost to follow-up if they repeatedly fail to return for scheduled visits and is unable to be contacted by the study site.

The following actions must be taken if a participant fails to return to the clinic for a required study visit:

- The site must attempt to contact the participant and reschedule the missed visit as soon as possible and counsel the participant on the importance of maintaining the assigned visit schedule and ascertain whether or not the participant wishes to and/or should continue in the study.
- Before a participant is deemed lost to follow-up, the investigator or designee must
 make every effort to regain contact with the participant (where possible, 3 telephone
 calls and, if necessary, a certified letter to the participant's last known mailing address
 or local equivalent methods). These contact attempts should be documented in the
 participant's medical record.
- Should the participant continue to be unreachable, they will be considered to have withdrawn from the study.

8. STUDY ASSESSMENTS AND PROCEDURES

See Appendix B for COVID-19-related guidance.

Note: Upon implementation of Protocol Amendment 2, protocol-required procedures have been reduced for ongoing participants.

8.1. Administrative and General Procedures

8.1.1. Informed Consent Process

- The investigator or their representative will explain the nature of the study to the participant or their legally authorized representative and answer all questions regarding the study.
 - Informed consent must be obtained before any study-related procedures are conducted, unless otherwise specified by the Protocol.
 - Informed consent must be obtained using the IRB/IEC-approved version in a language that is native and understandable to the participant. An ICF template will be provided by the sponsor or its designee. The sponsor or its designee must review and acknowledge the site-specific changes to the ICF template. The ICF must include a statement that the sponsor or its designee and regulatory authorities have direct access to participant records.
 - The ICF must contain all required elements and describe the nature, scope, and possible consequences of the study in a form understandable to the study participant.
- Participants must be informed that their participation is voluntary. Participants or their legally authorized representative will be required to sign a statement of informed consent that meets the applicable requirements and regulations for the countries in which the study is being conducted as well as the IRB/IEC or study center.
- The participant must be informed that their personal study-related data will be used by the sponsor in accordance with local data protection laws. The level of disclosure must also be explained to the participant.
- The participant must be informed that their medical records may be examined by Clinical Quality Assurance auditors or other authorized personnel appointed by the sponsor, by appropriate IRB/IEC members, and by inspectors from regulatory authorities.
- The medical record must include a statement that written informed consent was obtained before the participant was enrolled in the study and the date the written consent was obtained. The authorized person obtaining the informed consent must also sign the ICF.
- Participants must provide consent to the most current version of the ICF during their participation in the study.
- A copy of the ICF(s) must be provided to the participant or the participant's legally authorized representative

• A participant who is rescreened is not required to sign another ICF if the rescreening occurs within 30 days from the previous ICF signature date.

8.1.2. Screening Procedures

Screening is the interval between signing the ICF and the day the participant is randomized in the study. Screening may not exceed 32 days. Assessments that are required to demonstrate eligibility may be performed over the course of 1 or more days during the screening process. Central laboratory results will be used to determine eligibility unless otherwise stated (see Section 5.2 and Section 8.4.5). Hepatitis tests should be performed early in the screening process due to the length of time needed to obtain the results.

Results from the screening visit evaluations will be reviewed to confirm eligibility before randomization or the administration of study drug. Tests with results that fail eligibility requirements may be repeated once during screening if the investigator believes the results to be in error. For screening assessments that are repeated, the most recent available result before randomization will be used to determine eligibility.

See Sections 5.4 for information regarding screen failures.

8.1.3. Interactive Response Technology Procedure

Each participant will be identified in the study by a participant ID number, which is a combination of the 2-letter alpha country International Standards Organization code then a 3-digit site number, followed by a 3-digit participant number. Site staff should contact the IRT to obtain the participant ID number during screening. Upon determining that the participant is eligible for randomization, the IRT will be contacted to obtain the treatment assignment. Additionally, the IRT will be contacted at the study visits detailed in Table 3, Table 4, and Table 5 to update the study drug supply. Additional details are provided in the IRT Manual.

8.1.4. Distribution of Reminder Cards and Diaries

Participants will be provided with a reminder card at each visit. The reminder card will indicate the date/time of the next visit and will also remind the participant that they should not take their morning dose of study drug before coming to the clinic and they should record the most recent meal or snack in the diary (see Section 8.5).

Participants will be instructed on the use of the diary. The date and time of the last dose of study drug and the time of the most recent snack/ meal (see Section 8.5 and Table 12) will be recorded in the diary and captured in the eCRF. Daily study drug administration and any concomitant corticosteroid use will be recorded in the diary and verified by the investigators or designee at study visits as shown in Table 3, Table 4, and Table 5.

8.1.5. Demography and Medical History

8.1.5.1. Demographics and General Medical History

Demographic data and general medical history will be collected as permitted by local regulations at screening by the investigator or qualified designee and will include year of birth/age, race, ethnicity, medical and surgical history, and current illnesses. Medical history will include

relevant medical or surgical treatment within the last 10 years that are considered to be clinically significant by the investigator.

8.1.5.2. Disease Characteristics and Treatment History

A disease-targeted medical and treatment history including date of diagnosis of primary wAIHA, serological test, prior treatment history (all known failed treatments and all treatments within the prior year), number of transfusions within the prior year, number of hospitalizations due to AIHA within the prior year, and symptoms of wAIHA will be collected at screening.

8.2. Efficacy Assessments

Note: Upon implementation of Protocol Amendment 2, the efficacy assessments noted herein will be reduced as detailed in Table 3 and Table 4.

8.2.1. Hemoglobin Level, and Direct Antiglobulin Test

Participants will undergo hematology and a DAT to evaluate type of AIHA diagnosis and disease status as detailed in Table 3, Table 4, and Table 5. Prior documentation of DAT results are acceptable for study entry (see Section 5.1).

Note: The participants' screening hemoglobin enrollment eligibility will be based on a local laboratory assessment. If hemoglobin and other laboratory values are required for the immediate participant management, it is acceptable to use a local laboratory.

8.3. Patient-Reported Outcomes

Patient reported outcomes will be captured using an electronic PRO device.

[figure not shown]
Note: Upon implementation of Protocol Amendment 2, the PROs noted herein will no longer be required.

[figure not shown]
8.3.1. Functional Assessment of Chronic Illness Therapy – Fatigue

[figure not shown]
The FACIT-F is a 13-item measure that assesses self-reported fatigue and its impact upon daily activities and function over the past 7 days. The questionnaire should be completed by the participant using an electronic platform before any procedures are performed at the visits specified Table 3, Table 4, and Table 5. Additionally, the questionnaire must be completed before all other PRO assessments.

8.3.2. Six-Minute Walk Test

The 6MWT is used to evaluate submaximal exercise capacity (ATS 2002). It is a self-paced measurement of the distance that a participant can quickly walk on a flat, hard surface in a period of 6 minutes. The test should be performed after all other PRO assessments have been completed as detailed in the Study Manual and at the visits specified in Table 3 and Table 4. Approximately 10 minutes before and within 5 minutes after the 6MWT is performed, vital signs (blood pressure, pulse, and respiration) should be assessed.

8.4. Safety Assessments

8.4.1. Adverse Events

Adverse events will be monitored from the time the participant signs the ICF until at least 12 weeks after the last dose of study drug. Adverse events for enrolled participants that begin or worsen after informed consent should be recorded on the Adverse Events Form in the eCRF regardless of the assumption of a causal relationship with the study drug. Conditions that were already present at the time of informed consent should be recorded on the Medical History Form in the eCRF. Adverse events (including laboratory abnormalities that constitute AEs) should be described using a diagnosis whenever possible rather than by individual underlying signs and symptoms.

Adverse events will be reported by the participant (or, when appropriate, by a caregiver, surrogate, or the participant's legally authorized representative). The investigator and any qualified designees are responsible for detecting, documenting, and recording events that meet the definition of an AE or SAE and remain responsible for following-up on AEs that are serious, that are considered related to the study drug/procedures, or that caused the participant to discontinue the study drug. Care will be taken not to introduce bias when detecting AEs and/or SAEs. Open-ended and nonleading verbal questioning of the participant, such as "How are you feeling?", is the preferred method to inquire about AE occurrences. Adverse events may also be detected when they are volunteered by the participant during the screening process or between visits or through physical examinations, laboratory tests, or other assessments. The definition, reporting, and recording requirements for AEs are described in Section 9.

All SAEs will be reported to the sponsor or designee within 24 hours (immediately in Germany). The investigator will submit any updated SAE data to the sponsor within 24 hours (immediately in Germany) of it being available.

After the initial AE/SAE report, the investigator is required to proactively follow each participant at subsequent visits/contacts. All SAEs will be followed until resolution, stabilization, the event is otherwise explained, or the participant is lost to follow-up (as defined in Section 7.3).

At remote visits, adverse events will also be assessed via a phone call conducted by the study site, except for countries where remote visits are not permitted by local laws and/or regulations (see Table 3, Table 4, and Table 5).

8.4.2. Physical Examinations

Physical examinations must be performed by a medically qualified individual, such as a licensed physician, physician's assistant, or an advanced registered nurse practitioner, as local law permits at the visits detailed in Table 3, Table 4, and Table 5. Abnormalities identified after the first dose of study treatment constitute an AE if they are considered clinically meaningful, induce clinical signs or symptoms, require concomitant therapy, or require changes in study drug. Investigators should pay special attention to clinical signs related to previous serious illnesses.

The comprehensive physical examination will include height and body weight, and assessment(s) of the following organ or body systems: skin; head, eyes, ears, nose, and throat; thyroid; lungs; cardiovascular system; abdomen (liver, spleen); extremities; and lymph nodes; as well as a brief neurological examination.

A targeted physical examination should be conducted as indicated by symptoms reported by the participant, AEs, or other findings. Abnormalities that are considered clinically significant in the judgment of the investigator (or designee) are to be reported as AEs.

During the study, participants will be assessed by the investigator or medically qualified designee per institutional standard of care. These assessments should be an evaluation as indicated by participant symptoms, AEs, or other findings and documented on the AE eCRF.

8.4.3. Vital Signs

Vital sign measurements (to be taken before blood collection for laboratory tests), include blood pressure, pulse, respiratory rate, and body temperature. If vital signs cannot be taken before blood collection for laboratory tests, there must be a minimum of 30 minutes from the completion of the blood collection procedures to the beginning of the vital signs collection. Blood pressure and pulse will be taken with the participant in the recumbent, semirecumbent, or sitting position after 5 minutes of rest.

Abnormal vital sign results identified after the first dose of study drug constitute an AE if they are considered clinically meaningful, induce clinical signs or symptoms, require concomitant therapy, or require changes in study drug.

8.4.4. Electrocardiograms

Single 12-lead ECGs will be obtained as outlined in the SoA (see Table 3 and Table 4) using an ECG machine that automatically calculates the heart rate and measures PR, QRS, QT, and QTcF intervals. All 12-lead ECGs will be performed with the participant in a recumbent or semirecumbent position after 5 minutes of rest.

The 12-lead ECGs will be interpreted by the investigator at the site to be used for immediate participant management. Additional 12-lead ECGs may be performed as clinically indicated to manage participant safety. The decision to include or exclude a participant or discontinue study treatment based on an ECG flagged as "Abnormal, Clinically Significant" is the responsibility of the investigator, in consultation with the sponsor's medical monitor as appropriate. Clinically notable abnormalities that are considered clinically significant in the judgment of the investigator are to be reported as AEs. In the event that a single QTc is > 470 milliseconds at screening, the participant may enroll if the average QTc for triplicate ECGs conducted over a brief period is ≤ 470 milliseconds or with approval from the medical monitor. For participants with an intraventricular conduction delay (QRS interval > 120 milliseconds) at screening, the JTc interval may be used in place of the QTc with medical monitor approval. In addition, the JTc interval should be used for all subsequent assessments.

8.4.5. Laboratory Assessments

See Table 11 for the list of clinical laboratory tests to be performed and Table 3, Table 4, and Table 5 for the timing and frequency. A central laboratory will perform all clinical laboratory assessments for safety (ie, blood chemistries, hematology assessments, coagulation tests, endocrine function, and urinalysis). Additional testing may be required by the sponsor based on emerging safety data. All Protocol-required laboratory assessments must be conducted in accordance with the Laboratory Manual and Table 3, Table 4, and Table 5.

Note: The participants' screening hemoglobin enrollment eligibility will be based on a local laboratory assessment. Additionally, if the central laboratory is unable to perform any other required screening tests due to hemolysis related to wAIHA or the analytical method, then local laboratory test results may be used to determine participant eligibility.

At-home blood collection will be conducted during remote visits, except for countries where remote visits are not permitted by local laws and/or regulations (see Table 3 and Table 4). At-home sampling for additional laboratory assessments may also be conducted, except for countries where remote visits are not permitted by local laws and/or regulations; see Appendix B for COVID-19—related guidance. Information regarding collection, processing, and shipping of samples for laboratory assessment is provided in the Laboratory Manual.

Clinically significant abnormal laboratory findings are those that are not associated with the underlying disease, unless judged by the investigator to be more severe than expected for the participant's condition. All laboratory tests with values considered clinically significantly abnormal during participation in the study or within 30 days after the last dose of study drug should be repeated until the values return to normal or baseline or are no longer considered clinically significant by the investigator or medical monitor.

If screening laboratory assessments are performed more than 32 days before Day 1, then the tests must be repeated and eligibility confirmed before study drug administration on Day 1.

Laboratory sample collection on Day 1 must be performed before study drug administration.

See Section 9.1 for information regarding laboratory abnormalities that should be recorded as an AE in the eCRF.

Table 11: Required Laboratory Analytes

Chemistrya	Hematology ^{a,b}	Urinalysis With Microscopic Examination	Canalagu	Coogulation
, , , , , , , , , , , , , , , , , , ,	8,		Serology	Coagulation
Albumin	Complete blood count,	Color and appearance	CMV	D-dimer
Alkaline phosphatase	including:	pH and specific gravity	Hepatitis B surface antigen	
ALT	Hemoglobin	Bilirubin	Hepatitis B surface antigen	
AST	Hematocrit	Glucose	antibody	
Bicarbonate ^c	Platelet count	Ketones	Hepatitis B core antibody	
Blood urea nitrogen	Red blood cell count	Leukocytes	HBV-DNA	
Calcium	White blood cell count	Nitrite	HCV antibody	
Chloride		Occult blood	HCV-RNA	
Creatinine	Differential count, including:	Protein	HIV ^e	
Ferritin (screening visit and repeat at	Basophils	Urobilinogen		
Week 6 if participant has ongoing	Eosinophils			Pregnancy Testing
transfusion requirements)	Lymphocytes			Female participants of
Folic acid (screening visit only)	Monocytes			childbearing potential only
Glucose	Neutrophils			require a serum test at
				screening and EOT and a urine
Iron (screening visit and repeat at Week 6	Absolute values must be			pregnancy test before the first
if participant has ongoing transfusion	provided for:			dose on Day 1 and monthly
requirements)	WBC differential laboratory	D.	AT	during the study.
	results	DAT for IgG and C3d		Pregnancy tests (serum or
Phosphate		Other As	ssessments	urine) should be repeated if
Potassium		Vitamin B12 (screening visit or	nlv)	required by local regulations.
Sodium		Vitalinii B12 (sereciniig visit oi.	,	
Total protein		FSH		
Total iron-binding capacity (screening visit		1311		
and repeat at Week 6 if participant has				
ongoing transfusion requirements)				
Uric acid				

Note: Additional tests may be required, as agreed by investigator and sponsor, based on emerging safety data.

VV-CLIN-014098 CONFIDENTIAL

^a Chemistry and hematology parameters may be managed in real-time by local laboratory assessments.

b Hematology panels need to be performed in accordance with the standard of care at each investigational site for the participant's condition and monitoring at the investigator's discretion.

^c Bicarbonate not applicable in Japan.

^e HIV screening test is optional for participants enrolled in the US.

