6MWT		X									X	Vital signs should be conducted pre- and post-test. 6MWT must be performed after all other PRO assessments are completed. Section 8.3.2

Table 3: Schedule of Activities (Double-Blind) (Continued)

	Screening		Double-Blind Treatment Period									
	Day -32		W2	W4	W6	W8	W10	W12	W16	W20	EOT1a/EOSb	
Visit Day (Range)	to -1	Day 1	$\pm 3 d$	$\pm 3 d$	$\pm 3 d$	$\pm 3 d$	$\pm 3 d$	$\pm 3 d$	$\pm 3 d$	$\pm 3 d$	$W24 \pm 3 d$	Notes and Protocol Section

^a Participants receiving parsaclisib who permanently discontinue study drug will enter the post-treatment follow-up period (see Table 4 and Section 8.10).

VV-CLIN-014098 CONFIDENTIAL

^b Participants receiving placebo who permanently discontinue study drug will no longer be required to enter the post-treatment follow-up period and will perform EOT1/EOS upon discontinuation of treatment.

^c Fasting is not required for central laboratory assessments.

 Table 4:
 Schedule of Activities (Open-Label)

		1	o	pen-Lab	el Treat	ment				st-Treatm Follow-U _l		
Visit Day (Range)	W26 ± 3 d	W28 ± 5 d	W30 ± 5 d	W32 ± 5 d	W36 ± 5 d	W40 ± 5 d	W44 ± 5 d	EOT2 W48 ± 5 d	FUP1a/ EOS	FUP2b	FUP3 ^b	Notes and Protocol Section
In-office visit		X		X	X	X	X	X	X		X	
Remote visit	X		X							X		May be performed in-office at the discretion of the investigator. Note: Where local laws and/or regulations do not permit remote visits, these assessments will be performed in office.
Administrative procedures												
Prior/concomitant medications	X	X	X	X	X	X	X	X	X	X	X	Section 6.7
Contact IRT		X		X	X	X	X	X	X		X	Section 8.1.3
Distribute reminder cards		X		X	X	X	X	X				Section 8.1.4
Dispense study drug		X		X	X	X	X	X*				*Participants continuing into long-term extension. Section 6.1 and Section 8.1.3
Study drug return, accountability and compliance assessment		X		X	X	X	X	X				Section 6.4
Prophylactic treatment for PJP				As presc	ribed by	the invest	igator thro	oughout st	udy			Section 6.7.1.1
Healthcare resource utilization*		X		X	X	X	X	X			X	*No longer required upon implementation of Protocol Amendment 2.
Safety assessments												
AE assessments	X	X	X	X	X	X	X	X	X	X	X	Section 8.4.1
Comprehensive physical examination						_		X	X		X	Section 8.4.2
Targeted physical examination		X		X	X	X	X					Section 8.4.2
Vital signs	X	X	X	X	X	X	X	X	X	X	X	Section 8.4.3
12-lead ECG								X				Section 8.4.4

Table 4: Schedule of Activities (Open-Label) (Continued)

			0	pen-Lab	el Treat	ment				st-Treatm Follow-Uj		

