Visit Day (Range)	W26 ± 3 d	W28 ± 5 d	W30 ± 5 d	W32 ± 5 d	W36 ± 5 d	W40 ± 5 d	W44 ± 5 d	EOT2 W48 ± 5 d	FUP1a/ EOS	FUP2 ^b	FUP3 ^b	Notes and Protocol Section
Efficacy assessments	1	ı		1								
Hematology	X*	X	X*	X	X	X	X	X	X	X	X	*No longer required upon implementation of Protocol Amendment 2.
DAT								X				Section 8.2.1 and Section 8.4.5
PRO and clinical outcome asses	sments (Note: U	pon imp	olementa	tion of P	rotocol A	mendme	nt 2, the l	PROs note	d herein	will no lo	
FACIT-F scale		X		X		X		X			X	Should be completed before any other assessments. Must be completed before all other PRO assessments. Section 8.3.1

Table 4: Schedule of Activities (Open-Label) (Continued)

			0	pen-Lab	el Treat	ment				st-Treatm Follow-Uj		
	W26	W28	W30	W32	W36	W40	W44	EOT2 W48	FUP1a/	THE	ELIDAL	
Visit Day (Range) PRO and clinical outcome assess	±3 d	±5d	± 5 d	±5d	±5d	±5d	±5d	±5d	EOS	FUP2b	FUP3b	Notes and Protocol Section
6MWT	sments (continue	u) (Note	: Ороп	пприете	псистоп о	Protoco	X	ment 2, the	e PROS III	X	Vital signs should be conducted pre- and post-test. 6MWT must be performed after all other PRO assessments are completed. Section 8.3.2
Laboratory assessments ^c D-dimer		X		X	X		X	X				Section 8.4.5
Serum pregnancy								X			X	WOCBP only. Section 8.4.5.1
Urine pregnancy		X		X		X			X	X		WOCBP only. Section 8.4.5.1
Serum chemistry CMV		X		X	X X*	X	X	X	X	X	X	Section 8.4.5 *Monitor as clinically indicated

a Only required for participants receiving parsaclisib; post-treatment follow-up visit to be conducted 4 weeks (± 5 days) after EOT visit (or after the last dose of study drug if the EOT visit was not performed).

^b No longer required upon implementation of Protocol Amendment 2.

^c Fasting is not required for central laboratory assessments.

 Table 5:
 Schedule of Activities (Long-Term Extension)

		Long-Tern			
Visit Day (Range)	W56 (± 7 d)	Every 8 Weeks (± 7 d)	Every 16 Weeks (± 7 d)	EOT3a	Notes and Protocol Section
In-office visit	X	X		X	
Administrative procedures					·
Contact IRT	X	X		X	Section 8.1.3
Prior/concomitant medications	X	X		X	Section 6.7
Distribute reminder cards	X	X		X	Section 8.1.4
Dispense study drug	X	X			Section 6.1 and Section 8.1.3
Study drug return, accountability and compliance assessment	X	X		X	Section 6.4
Prophylactic treatment for PJP		As prescribed by the inve	estigator throughout study		Section 6.7.1.1
Healthcare resource utilization	X		X	X	Section 8.3.8
Safety assessments		-	1		
Comprehensive physical examination				X	Section 8.4.2

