8.4.5.1. Pregnancy Testing

A serum pregnancy test will be required for all WOCBP during screening (before the first dose of study drug) and at the visits indicated in Table 3, Table 4, and Table 5. Urine pregnancy tests will be performed locally as outlined in Table 3, Table 4, and Table 5 as medically indicated (eg, in case of loss of menstrual cycle, when pregnancy is suspected), or per country-specific requirement (note that country required- urine pregnancy testing will be outlined and communicated to investigational sites under separate cover). If a urine pregnancy test is positive, the results should be confirmed with a serum pregnancy test.

[figure not shown]
If the serum pregnancy test is negative after a urine test was positive, the investigator will assess the potential benefit/risk to the participant and determine whether it is in the participant's best interest to resume study drug and continue participation in the study.

If a pregnancy is confirmed by a serum pregnancy test, the participant should be instructed to immediately discontinue study drug (see Section 9.8 for procedures and reporting requirements).

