## 1. INTRODUCTION

This is a Phase 3, multicenter, randomized, double-blind, placebo-controlled study to evaluate the efficacy and safety of parsaclisib 2.5 mg QD compared with placebo over a 24-week double-blind treatment period followed by a 24-week open-label treatment period of parsaclisib. Participants may then continue to receive parsaclisib in a long-term extension period.

On 17 APR 2023, Incyte decided to terminate this Phase 3 study. The decision was based on the change in the regulatory landscape for Pi3k-delta inhibitors combined with enrollment challenges. At the time of this decision, 13 participants had been randomized and received study drug in this study.

The purpose of this SAP is to provide details of the statistical analyses that have been outlined in the INCB 50465-309 Protocol. The scope of this plan includes the final analyses, which will be executed by the Department of Biostatistics or designee.

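### Table 11 asks for monthly urine pregnancy tests, but the schedules of activities space scheduled tests 8 weeks apart from Week 32 onward

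*Protocol*

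**What the plan says.** Table 11 in Protocol Section 8.4.5 states, for women of childbearing potential, a serum pregnancy test at screening and at end of treatment, and a urine test before the first "dose on Day 1 and monthly" while the study runs. It makes no exception for the open-label period or the long-term extension.

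The body of Section 8.4.5 refers the reader to "Table 3, Table 4, and Table 5 for the timing and frequency". Section 8.4.5.1 does the same: "Urine pregnancy tests will be performed locally as outlined in Table 3, Table 4, and Table 5 as medically indicated", with further tests where a country requires them. It does not mention a monthly interval. On the country requirements it says that "urine pregnancy testing will be outlined and communicated to investigational sites under separate cover", so they are not in these documents.

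The schedules themselves read as follows:

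- **Table 3 (double-blind):** urine on Day 1 and at Weeks 4, 8, 12, 16 and 20; serum at screening and Week 24.
- **Table 4 (open-label):** the "Urine pregnancy" row is marked on treatment at Weeks 28, 32 and 40 only; serum at Week 48. The "Dispense study drug" row is marked at Weeks 28, 32, 36, 40, 44 and 48, all of them in-office visits.
- **Table 5 (extension):** urine at Week 56 and then every 8 weeks; serum at end of treatment.

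**The concern.** The protocol gives two different frequencies for the same safety test, and the less frequent one is what sites will follow. A confirmed pregnancy requires study drug to be stopped at once (Sections 8.4.5.1 and 9.8), so the interval between scheduled tests limits how long an unsuspected pregnancy can go on under exposure. After Week 32 a participant can be handed new drug at Weeks 36 and 44 without the test that Table 11 says she should have had.

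Two features of the protocol give this some weight. Under Amendment 2, participants on placebo may start parsaclisib before Week 24 and then move to Table 4, so that schedule also covers people newly exposed to active drug. And note d of Appendix A says it is not known whether study drug interferes with hormonal contraception. There is also a housekeeping consequence: SAP Section 6.3 summarizes and lists protocol deviations, and with two stated frequencies it is unclear whether a missing monthly test counts as one.

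**Working it through.** **Inputs.** Test visits come from the urine and serum rows of Tables 3, 4 and 5. Visit windows come from the same tables: ± 3 days through Week 24, ± 5 days at Weeks 28 to 48, ± 7 days in the extension. A test of either type counts as a pregnancy test. Monthly is read as every 4 weeks, or 28 days.

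**Step 1: scheduled tests.** Combining urine and serum, tests fall on Day 1 and at Weeks 4, 8, 12, 16, 20, 24, 28, 32, 40, 48 and 56, then every 8 weeks.

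**Step 2: does the monthly figure reproduce?** Day 1 to Week 32 gives 8 gaps of 4 weeks, so it does up to that point. The widest window effect is between Weeks 28 and 32: 28 ± (5 + 5) = 18 to 38 days.

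**Step 3: from Week 32.** The formula is nominal gap ± (window of first visit + window of second visit).

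| Interval | Nominal gap (days) | Windows | Range (days) |
|---|---|---|---|
| Week 32 to 40, Week 40 to 48 | 56 | 5 + 5 | 46 to 66 |
| Week 48 to 56 | 56 | 5 + 7 | 44 to 68 |
| Between extension visits | 56 | 7 + 7 | 42 to 70 |

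Every nominal gap is 56 / 28 = 2 times the 4-week interval. Even the shortest gap the windows allow, 42 days, is longer than any calendar month, so reading monthly as a calendar month changes nothing.

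**Step 4: urine tests alone.** Table 11's monthly rule is written for urine tests. Without the Week 48 serum test, the gap from Week 40 to Week 56 would be 16 weeks. Counting the serum test is the reading more favourable to the protocol.

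**Step 5: is it a table-reading error or a deliberate cut?** The in-office and dispensing rows of Table 4 line up with the same visit headers and do show Weeks 36 and 44, so the blanks in the urine row are not an extraction fault. Procedures dropped by Amendment 2 are marked as no longer required; the on-treatment pregnancy rows carry no such mark.

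**Step 6: the fix.** With tests added at Weeks 36 and 44, all gaps through Week 48 are 28 days, 18 to 38 days at the widest windows.

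**The case against.** The best reply is that the protocol says which text governs. Section 8.4.5 uses Table 11 for the list of analytes and Tables 3 to 5 for timing, and Section 8.4.5.1, which deals specifically with pregnancy testing, also points to the schedules. On that reading monthly is loose wording in one cell, a site that follows the schedule is compliant, and the whole matter is a wording mismatch. Nothing in the documents shows that 8-weekly testing after 32 weeks of 4-weekly testing is unsafe, and accepting 8 weeks in the extension weakens any claim that it is unsafe in Weeks 32 to 48.

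There are other safeguards. Tests are done when pregnancy is suspected or a period is missed, some countries may require more, and contraception is required until 90 days after the last dose, with a second method for users of hormonal contraception. The end-of-treatment serum test closes the last interval whenever drug is stopped, and a participant on a drug holiday in the extension is off drug. In Table 5 the dispensing visits at Week 56 and every 8 weeks each carry a urine test, so dispensing at a scheduled visit without a test is confined to Weeks 36 and 44.

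Most of this stands, and it keeps the point small. It does not reconcile the two frequencies. That the schedules govern timing means only that the sparser version is carried out while the stricter statement stays in the protocol. Testing on suspicion depends on someone suspecting; a scheduled test does not. Country rules that are not in the documents cannot be assumed to apply everywhere.

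**Conclusion.** The concern holds, at minor severity. The stated monthly frequency is met through Week 32 and not after it, with windows stretching the doubled interval to at most 66 days in the open-label period, 68 days across the move to the extension, and 70 days within it.

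This rests on counting serum and urine tests alike and on no additional country-specific testing; where such testing applies, the interval may be shorter. The number of people affected is small and not stated. The SAP Introduction records that when the sponsor decided to terminate the study "13 participants had been randomized and received study drug in this study", and neither document says how many women of childbearing potential continued past Week 32. The matter is one of participant safety and protocol consistency; it has no bearing on any endpoint, the sample size or the analysis.

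**What to change.** 1. **Table 4, urine pregnancy row:** add a local urine test at Weeks 36 and 44. The cost is two urine tests per woman of childbearing potential, with no new visits.
2. **Extension:** either amend Table 11 to state testing every 4 weeks through Week 48 and every 8 weeks during the long-term extension, or add a urine test to Table 5 at 4 weeks after each 8-weekly visit. The first is a wording change only. The second costs one extra test per 8 weeks at a time when no visit is scheduled, so the rewording is an acceptable choice.

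Rewording Table 11 simply to follow the schedules would remove the inconsistency but leave drug dispensed at Weeks 36 and 44 without a test. The added tests are preferable there because they cost so little.
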